2.1. Time and Events Table – Part A (Cohort 1) 2.2. Time and Events Table – Part B (Cohorts 2-4) 6.2. Exclusion Criteria 12.2.	‘Cotinine Screen’ has been changed to ‘Smoking Screen’ and ‘Cotinine Breath Test’ has been changed to ‘Smoking Breath Test’ in Section 2.1. and Section 2.2. Carbon monoxide levels have been included in Exclusion Criteria 24. In the ‘Other Screening Tests’ section, ‘Cotinine Breath Test’ has	The ‘Cotinine Breath Test’ either includes urine cotinine and/or smoking breath test. The study will determine evidence of current smoking using a non-invasive breath carbon monoxide (CO) test device, which will provide CO levels to determine evidence of smoking.

Section # and Name	Description of Change	Brief Rationale
Appendix 2: Clinical Laboratory Tests	been changed to 'Smoking Breath Test'.	

2.1. Time and Events Table – Part A (Cohort 1)
 
2.2. Time and Events Table – Part B (Cohorts 2-4)
 
12.2. Appendix 2: Clinical Laboratory Tests
	
In Part A of the study, Haem/Chem/Urinalysis assessments can be non-fasted for Day -1 and the Follow-Up Visit.
 
In Part B of the study Haem/Chem/Urinalysis assessments can be non-fasted for Day -1 only.
 
Additional wording included to Note 2 in Table 3 - Non-fasted samples can be collected on Day -1 (All Parts) and at the Follow-Up visit (Part A Only).
	
The fasting lipid panel in Part B was separated out in the SoA since it was noted to be performed on Day -1 or Day 1. This was moved to Day 1 only since subjects will not be fasted on Day -1. The 4β-hydroxycholesterol will be checked on Day 1, as a fasted sample.
 
It is recommended that all other lab time points being performed (inclusive of the follow-up visit) are to be performed under fasted conditions since this is essential to assess lipid profiles.

6.2. Exclusion Criteria	An additional Exclusion Criteria (16) has been added. "The subject has participated in a clinical trial and has received an investigational product within the following time period prior to the first dosing day in the current study: 30 days, 5 half-lives or twice the duration of the biological effect of the investigational product (whichever is longer). All subsequent exclusion criteria numbers have increased by 1.	To define the minimum length of time since a subject was last exposed to a new chemical entity.

2.1. Time and Events Table – Part A (Cohort 1)
 
2.2. Time and Events Table – Part B (Cohorts 2-4)
 
7.2. Method of Treatment
	
Updated wording in the 'Notes' section under the procedure "Randomization" in Section 2.1. and Section 2.2 to state:
 
"Randomization can occur on either Day -1 or Day 1 in both Parts A and B of the study."
 
Updated wording to include that randomization can take place on Day -1 or Day 1 in Section 7.2.
	
There was a discrepancy in the SoA under the procedure "Randomization" in both Part A and B on Day -1 and Section 7.2.
 
Randomization can take place on either Day -1 or Day 1.

Section # and Name	Description of Change	Brief Rationale
Assignment		
9.3.3. Vital Signs	The semi-supine position has been removed from this section.	To remove any ambiguity with this assessment, the supine position will be the only position used to assess vital signs.
2.2. Time and Events Table – Part B (Cohorts 2-4)	A comment has been added to the Meals row to state that “Meals will be served as per the site schedule on Days -1, 16 and 17.”	Clarification of the wording for the meal schedule on non-dosing and non PK sampling days.
2.2. Time and Events Table – Part B (Cohorts 2-4)	Superscript ‘g’ has been removed from the PK blood sampling on Day 1.	Superscript ‘g’ refers to study assessments on Day 14 of the protocol and not Day 1. This is a correction of a typographical error.
6.2. Exclusion Criteria	Update of the wording in Exclusion Criteria 3 to change the definition of what constitutes a positive tuberculin skin test from <5 mm skin induration at 48 to 72 hours to >5 mm skin induration at 48 to 72 hours.	Correction of a typographical error. An induration of >5 mm skin induration at 48 to 72 hours is considered a positive TB test.
7.2. Method of Treatment Assignment	The Method of Treatment Assignment has been updated to note that subjects in Cohort 1 will be randomized to 1 of 4 treatment sequences rather than 1 of 3. The additional treatment sequence (ABC) has been added.	Correction of a typographical error. There is no change to the randomization ratio, which is 3:1.
2.1. Time and Events Table – Part A (Cohort 1)	Removal of the 10hr time interval post-last dose in note ‘b’ for TID dosing. This now reads “ TID dosing: GSK2982772 or placebo will be administered using a 7hr, 7hr dosing interval.”	Correction of a typographical error. Since Part A is a single-day of dosing, this 10hr interval has been removed.
2.2. Time and Events Table – Part B (Cohorts 2-4)	The Neurological Examination originally on Day 4 has been moved to Day 3.	Correction of a typographical error. 48hr post-first dose assessment would be on Day 3.
6.2. Exclusion Criteria	Exclusion Criteria 29 has been updated to state “Fasting total cholesterol” rather than “Total fasting cholesterol”.	Correction of typographical error.

Section # and Name	Description of Change	Brief Rationale
5.7. Dose Justification	The title in Figure 2 has been changed from "Monkey C _{max} " to "Monkey AUC(0-24)".	Correction of the PK parameter stated in the Figure 2 title.
12.4. Appendix 4: Adverse Events: Definitions and Procedures for Recording, Evaluating and Follow-Up Assessments	In the 'Reporting of SAE to GSK' section, facsimile transmission of the SAE paper CRF has been changed to email transmission.	Notification of an SAE via email is the preferred method of transmission to the Medical Monitor and SAE Coordinator.

1. INTRODUCTION

The purpose of this reporting and analysis plan (RAP) is to describe the analyses to be included in the Clinical Study Report for Protocol 205184:

Revision Chronology:				
2017N326600_00	31-JUL-2017	Original		
2017N326600_01	07-DEC-2017	Amendment 01		
2017N326600_02	15-FEB-2018	Amendment 02		
2017N326600_03	26-FEB-2018	Republished Amendment 02		

2. SUMMARY OF KEY PROTOCOL INFORMATION

2.1. Changes to the Protocol Defined Statistical Analysis Plan

Changes from the originally planned statistical analysis specified in the protocol are outlined in Table 1.

Table 1 Changes to Protocol Defined Analysis Plan

Protocol	Reporting & Analysis Plan	
Statistical Analysis Plan	Statistical Analysis Plan	Rationale for Changes
An interim analysis may be performed during the study on completed cohorts in Part A and Part B of the study to aid internal decision making only. The RAP will describe the planned interim analyses in greater detail.	No formal IA will be conducted during the study.	The DEC make decisions on proceeding to higher dose strengths based on assessment of safety, tolerability and pharmacokinetic data at the preceding dose only.
Protocol Section 10.3 references an 'Enrolled population'.	RAP uses the 'Randomised Population'.	The population was renamed to match the current IDSL guidance.

2.2. Study Objective(s) and Endpoint(s)

Objectives	Endpoints		
Primary Objectives	Primary Endpoints		
 To investigate the safety and tolerability of repeat doses of GSK2982772 in healthy subjects. 	 Adverse events. Clinical laboratory values (clinical chemistry, haematology and urinalysis). Vital sign measurements (blood pressure, heart rate, respiratory rate and body temperature). Physical examinations. 12-Lead ECG monitoring. 		

Objectives	Endpoints		
Secondary Objectives	Secondary Endpoints		
To characterise the pharmacokinetic (PK) profile of repeat doses of GSK2982772 in healthy subjects.	 A 24 hr profile to be collected on Day 1 of Part A and Day 14 of Part B. On Day 1 of Part B, the PK profile will be evaluated following the first dose only. Derived PK parameters for GSK2982772, including area under the plasma drug concentration versus time curve over 24 hr (AUC₍₀₋₂₄₎) and AUC over each dose interval (i.e. AUC₍₀₋₇₎, AUC₍₇₋₁₄₎ and AUC₍₁₄₋₂₄₎ for TID and AUC₍₀₋₁₂₎ and AUC_(12- 24) for BID). Maximum observed plasma drug concentration (C_{max}) following each dose, time to maximum observed plasma drug concentration (T_{max}) following each dose, observed trough plasma drug concentrations (C₀, C₇, C₁₄ and C₂₄ for TID dosing and C₀, C₁₂ and C₂₄ for BID dosing). 		
 To assess the impact of food on the PK of repeat doses of GSK2982772 in healthy subjects at steady state 	 Derived PK parameters for GSK2982772, including AUC₍₀₋₇₎, AUC₍₇₋₁₄₎, C_{max}, after 1st dose of day and T_{max} after 1st dose of day. 		
To assess potential effect of repeat doses of GSK2982772 on CYP3A4 enzyme activity	 Plasma 4β-hydroxycholesterol to cholesterol ratio pre- treatment and following 14 days of repeat dosing of GSK2982772. 		
Exploratory Objectives	Exploratory Endpoints		
• To investigate the levels of circulating glucuronide metabolite (M8; GSK3562183) and desmethyl metabolite (M9; GSK2997852) in healthy subjects after single-day and repeat dosing of GSK2982772.	 Quantify M8 (GSK3562183) and M9 (GSK2997852) in select plasma PK samples at pre-dose and 2 hr following Day 14 of repeat dosing of GSK2982772. 		

2.3. Study Design

Overview of Study Design and Key Features				
	ngle-Day Ascending Doses 1 Day 3:1 Randomized SK2982772:Placebo	Part B – Repeat Doses 14 Days 3:1 Randomized GSK2982772:Placebo	Part B – Repeat Doses 14 Days 9:5 Randomized GSK2982772:Placebo	
240 mg	Cohort 1 N=12 TID (1 Day) followed by, TID (1 Day) followed by, 60 mg BID (1 Day)	Cohort 2 N=12 120 mg TID 14 Days *	Cohort 3 N=14 120 mg TID 14 Days *	
			Cohort 4 N=14 240 mg TID 14 Days * Cohort 5 N=14	
			360 mg BID 14 Days	
Design		Effect Treatment ndomized, double-blind (spo	and the second	
Features	 controlled study to evalua GSK2982772 in repeat or This study consists of 2 p Part A (Cohort 1) – s way crossover. 	te the safety, tolerability and ral doses in healthy participal arts: ingle ascending dose, randor	pharmacokinetics of	
Time & Events	Refer to Appendix 2: Sch	edule of Activities		
Treatment Assignment	participants (9 active, 3 p	placebo) in Cohorts 1 and 2 (ipants with approximately 12 up to approximately 24 in total) , 4 and 5 (up to approximately	
	 If participants prematurely discontinue the study, additional replacement participants may be randomized in order to guarantee that sufficient participants are treated with GSK2982772 at any given dose before escalating to the following dose. Replacement participants will be assigned to the same treatment sequence (Cohort 1) or treatment (Cohorts 2-5). 			
	Response System (IVRS summarized in the Scher blinded study treatment,	ntrally randomized using an S/IWRS). Study treatment is o dule of Activities (SoA). Each labelled with his/her unique r turned study treatment shoul	dispensed at the study visits n participant is dispensed	

Overview of St	udy Design and Key Features
	 In Cohorts 1 and 2, participants will be randomized in a 3:1 ratio to either GSK2982772 or placebo. In Cohorts 3, 4 and 5, participants will be randomized in a 9:5 ratio to either GSK2982772 or placebo.
	 The randomization will reflect the fact that at least 2 of the 12 participants in Cohorts 1 and 2 and at least 2 of the 14 participants in Cohort 4 and 5 (one participant will receive GSK2982772 and one participant will receive matched-placebo) will be dosed first (on Day 1) in each part to enable dose staggering. In Cohort 1, the participants will be randomized to one of four sequences (ABC, ABP, APC, PBC), where the treatments are: A 120 mg TID B 240 mg TID C 360 mg BID P Placebo Once a treatment allocation number has been assigned to a participant, it cannot be reassigned to any other participant.
Dosing	 For TID dosing, GSK2982772 or placebo will be administered using a 7hr and 7hr dosing interval in Part A and a 7hr, 7hr and 10hr dosing interval in Part B. For BID dosing, GSK2982772 or placebo will be administered using a 12hr dosing interval.
Interim Analysis	 No interim analyses will be performed. The decision to proceed to higher dose strengths will be made by the Dose Escalation Committee (DEC) based on assessment of safety, tolerability and pharmacokinetic data at the preceding dose.

2.4. Statistical Hypotheses / Statistical Analyses

- The objectives of this study are to assess the safety and tolerability of single and repeat ascending doses of GSK2982772. No formal hypotheses will be tested.
- An estimation approach will be used to describe pharmacokinetics of GSK2982772, where point estimates and corresponding 90% confidence intervals will be constructed, unless otherwise stated.

3. PLANNED ANALYSES

3.1. Interim Analyses

No interim analyses will be performed. The decision to proceed to higher dose strengths will be made by the Dose Escalation Committee (DEC) based on assessment of safety, tolerability and pharmacokinetic data at the preceding dose.

3.2. Final Analyses

The final planned primary analyses will be performed after the completion of the following sequential steps:

- 1. All participants have completed the study as defined in the protocol.
- 2. All required database cleaning activities have been completed and final database release (DBR) and database freeze (DBF) has been declared by Data Management.
- 3. All criteria for unblinding the randomization codes have been met.
- 4. Randomization codes have been distributed according to RandAll NG procedures.

4. ANALYSIS POPULATIONS

Population	Definition / Criteria	Analyses Evaluated
All Subjects	 Comprises of all participant who were screened and allocated a subject number. 	 Screen Failure Population Analysed.
Randomised	 All participants who were randomly assigned to treatment in the study. This population will be based on the treatment the participant was randomized to. 	Age ranges
Safety	 Comprises of all randomised participants who received at least one dose of study treatment. This population will be based on the treatment the subject was randomised to. 	 All other Study Population Safety
Pharmacokinetic	• Participants in the 'Safety' population for whom a pharmacokinetic sample was obtained and analysed.	• PK

Refer to Appendix 10: List of Data Displays which details the population used for each display. Note: All data displays (Tables, Figures & Listings) will use the term "Subject" which reflects CDISC and GSK Data Display Standards terminology.

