10.3. Populations for Analyses

For purposes of analysis, the following populations are defined:

Population	Description
Enrolled	All participants who sign the ICF
Safety	All randomized participants who take at least 1 dose of study treatment. Participants will be analyzed according to the treatment they actually received.
PK	The 'PK Population' is defined as subjects in the 'Safety' population for whom a PK sample was obtained and analyzed.

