5. CONSIDERATIONS FOR DATA ANALYSES AND DATA HANDLING CONVENTIONS

5.1.	Study Treatment & Sub-grou	up Display Descriptors

Treatment Group Descriptions											
	RandAll NG	Data Displays for Reporting									
Code	Description	Description	Order in TLF								
Р	Placebo TID Single Dose	Placebo	1								
Q	Placebo BID Single Dose	Placebo	1								
Α	GSK2982772 120 mg TID Single Dose	GSK 120 mg TID	2								
В	GSK2982772 240 mg TID Single Dose	GSK 240 mg TID	3								
С	GSK2982772 360 mg BID Single Dose	GSK 360 mg BID	4								
R	Placebo TID Repeat Dose	Placebo	1								
S	Placebo BID Repeat Dose	Placebo	1								
D	GSK2982772 120 mg TID Repeat Dose	GSK 120 mg TID	2								
E	GSK2982772 240 mg TID Repeat Dose	GSK 240 mg TID	3								
F	GSK2982772 360 mg BID Repeat Dose	GSK 360 mg BID	4								
G	GSK2982772 Cohort 3 Repeat Dose	GSK 120 mg TID	2								
н	GSK2982772 Cohort 4 Repeat Dose	GSK 240 mg TID	3								
J	GSK2982772 Cohort 5 Repeat Dose	GSK XX mg TID/BID ^[1]	3 or 4								
Т	Placebo Cohort 3 Repeat Dose	Placebo	1								
U	Placebo Cohort 4 Repeat Dose	Placebo	1								
V	Placebo Cohort 5 Repeat Dose	Placebo	1								

NOTES:

^[1] Dose level not required as the study met the PK stopping criteria at the end of Cohort 4.

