10.5.2. Reporting Standards

General

• The current GSK Integrated Data Standards Library (IDSL) will be applied for reporting, unless otherwise stated (IDSL Standards Location: https://spope.gsk.com/sites/IDSLLibrary/SitePages/Home.aspx):

- 4.03 to 4.23: General Principles
- 5.01 to 5.08: Principles Related to Data Listings
- 6.01 to 6.11: Principles Related to Summary Tables
- 7.01 to 7.13: Principles Related to Graphics
- Do not include participant level listings in the main body of the GSK Clinical Study Report. All participant level listings should be located in the modular appendices as ICH or non-ICH listings.
- All data displays (Tables, Figures & Listings) will use the term "Subject" which reflects CDISC and GSK Data Display Standards terminology.

Formats

- All data will be reported according to the actual treatment the participant received, unless otherwise stated.
- GSK IDSL Statistical Principles (5.03 & 6.06.3) for decimal places (DP's) will be adopted for reporting of data based on the raw data collected, unless otherwise stated.
- Numeric data will be reported at the precision collected on the eCRF.
- The reported precision from non eCRF sources will follow the IDSL statistical principles but may be adjusted to a clinically interpretable number of DP's.

Planned and Actual Time

- Reporting for tables and figures:
 - Planned time relative to dosing will be used in figures and summaries and calculation of any derived parameters, unless otherwise stated.
 - The impact of any major deviation from the planned assessment times and/or scheduled visit days on the analyses and interpretation of the results will be assessed as appropriate.
- Reporting for Data Listings:
 - Planned and actual time relative to study drug dosing will be shown in listings (Refer to IDSL Statistical Principle 5.05.1).

Unscheduled	Unscheduled or unplanned readings will be presented within the participant's listings.								
Unscheduled Visits									
Unscheduled visi	 Unscheduled visits will not be included in summary tables and/or figures. 								
All unscheduled v	All unscheduled visits will be included in listings.								
Descriptive Summar	y Statistics								
Continuous Data	Refer to IDSL Statistical Principle 6.06.1								
Categorical Data	N, n, frequency, %								
Graphical Displays									
Refer to IDSL Statistical Principals 7.01 to 7.13.									

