10.10.4. Study Population Tables

Study F	Study Population Tables						
No.	Population	IDSL / Example Shell	Title	Programming Notes	Deliverable [Priority]		
Part A	Cohort 1 – sing	gle ascending dos	e, 3-way crossover): Subject Disposition				
1.1.	Safety (Part A)	ES1A	Summary of Subject Disposition for the Subject Conclusion Record (Part A)	ICH E3, FDAAA, EudraCT Add footnote: Note: "Subjects" is used to refer to "Participants" in all data displays to reflect GSK display standards and CDISC SDTM/ADaM standards.	SAC		
1.2.	Safety (Part A)	SD1	Summary of Treatment Status and Reasons for Discontinuation of Study Treatment (Part A)	ICH E3	SAC		
1.3.	Safety (Part A)	ES4	Summary of Disposition at Each Study Epoch (Part A)	ICH E3	SAC		
1.4.	All Subject (Part A)	ES6	Summary of Screening Status and Reasons for Screen Failure (Part A)	Journal Requirements	SAC		
Part A	Part A (Cohort 1 – single ascending dose, 3-way crossover): Protocol Deviation						
1.5.	Safety (Part A)	DV1	Summary of Important Protocol Deviations (Part A)	ICH E3	SAC		

Study F	Population Tabl	es			
No.	Population	IDSL / Example Shell	Title	Programming Notes	Deliverable [Priority]
Part A	Cohort 1 – sing	gle ascending dos	e, 3-way crossover): Population Analysed		
1.6.	All Subjects (Part A)	SP1	Summary of Study Populations (Part A)	 IDSL Add the following footnotes: [1] Subjects are included in the Randomised population if they were randomly assigned to treatment in the study. [2] Subjects are included in the Safety population if they have been randomized and received at least one dose of study treatment. [3] Subjects are included in the Pharmacokinetic population if they are in the Safety Population and a pharmacokinetic sample was obtained and analysed. 	SAC
Part A	(Cohort 1 – sing	gle ascending dos	e, 3-way crossover): Demographic and Baseline Characteris	tics	
1.7.	Safety (Part A)	DM3	Summary of Demographic Characteristics (Part A)	ICH E3, FDAAA, EudraCT Do not include Weight (to be included in Vital Signs summary) Add Footnote: [1] For calculating age, birth date is imputed as June 30 in the year of birth.	SAC

Study F	Population Tabl	es			
No.	Population	IDSL / Example Shell	Title	Programming Notes	Deliverable [Priority]
1.8.	Randomised (Part A)	DM11	Summary of Age Ranges (Part A)	EudraCT Only include age ranges applicable to the study ('Adult (18-64 years)' and '>=65-84 years')) Please add footnote to say that randomised population=enrolled population.	SAC

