10.10.9. ICH Listings

ICH: Lis	stings				
No.	Population	IDSL / Example Shell	Title	Programming Notes	Deliverable [Priority]
Part A (Cohort 1 – single a	scending dose,	3-way crossover): Subject Disposition		
1.	All Subjects (Part A)	ES7	Listing of Reasons for Screen Failure (Part A)	Journal Guidelines	SAC
2.	Safety (Part A)	ES3	Listing of Reasons for Study Withdrawal (Part A)	ICH E3	SAC
3.	Safety (Part A)	SD3	Listing of Reasons for Study Treatment Discontinuation (Part A)	ICH E3	SAC
4.	Safety (Part A)	BL2	Listing of Subjects for Whom the Treatment Blind was Broken (Part A)	ICH E3	SAC
5.	Safety (Part A)	TA1	Listing of Planned and Actual Treatments (Part A)	IDSL	SAC
Part A (Cohort 1 – single a	scending dose,	3-way crossover): Protocol Deviations	·	
6.	Safety (Part A)	DV2A	Listing of Important Protocol Deviations (Part A)	ICH E3	SAC
7.	Safety (Part A)	IE4	Listing of Subjects with Inclusion/Exclusion Criteria Deviations (Part A)	ICH E3	SAC
Part A (Cohort 1 – single a	scending dose,	3-way crossover): Populations Analysed		
8.	All Subjects (Part A)	SP3a	Listing of Subjects Excluded from Any Population (Part A)	ICH E3	SAC

ICH: Lis	tings				
No.	Population	IDSL / Example Shell	Title	Programming Notes	Deliverable [Priority]
Part A (Cohort 1 – single a	scending dose,	3-way crossover): Demographic and Baseline Characteristics		
9.	Safety (Part A)	DM4	Listing of Demographic Characteristics (Part A)	ICH E3 Do not include Weight.	SAC
10.	Safety (Part A)	DM10	Listing of Race (Part A)	ICH E3	SAC
Part A (Cohort 1 – single a	scending dose,	3-way crossover): Prior and Concomitant Medications	·	
11.	Safety (Part A)	CP_CM4	Listing of Concomitant Medications (Part A)	IDSL	SAC
Part A (Cohort 1 – single a	scending dose,	3-way crossover): Exposure and Treatment Compliance		
12.	Safety (Part A)	EX4	Listing of Exposure Data (Part A)	ICH E3	SAC
Part A (Cohort 1 – single a	scending dose,	3-way crossover): Adverse Events		
13.	Safety (Part A)	AE9CP	Listing of All Adverse Events (Part A)	ICH E3	SAC
14.	Safety (Part A)	AE7	Listing of Subject Numbers for Individual Adverse Events (Part A)	ICH E3	SAC
15.	Safety (Part A)	AE2	Listing of Relationship Between Adverse Event System Organ Classes, Preferred Terms, and Verbatim Text (Part A)	IDSL	SAC
Part A (Cohort 1 – single a	scending dose,	3-way crossover): Serious and Other Significant Adverse Even	nts	
16.	Safety (Part A)	AE9CPa	Listing of Serious Adverse Events (Part A)	ICH E3 Include fatal and non-fatal status	SAC

ICH: Lis	stings				

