28.	Safety (Part A)	EG4	Listing of ECG Values of Potential Clinical Importance (Part A)	IDSL Include absolute PCIs. Footnote: Note: H=High absolute value, L=Low absolute value. For QTc Interval H1= >450msec and <480msec, H2= >=480msec and <500msec, H3= >=500msec.	SAC			

ICH: Lis	tings				
No.	Population	IDSL / Example Shell	Title	Programming Notes	Deliverable [Priority]
29.	Safety (Part A)	EG4	Listing of ECG Changes of Potential Clinical Importance (Part A)	Include change from baseline PCIs. Footnote: Note: H=High change from baseline value, L=Low change from baseline value. For QTc Interval H1= >30msec and <=59msec, H2= >=60msec	SAC
30.	Safety (Part A)	EG6	Listing of All ECG Findings for Subjects with an Abnormal ECG Finding (Part A)	IDSL	SAC
31.	Safety (Part A)	EG6	Listing of Abnormal ECG Findings (Part A)	IDSL	SAC
Part A (Cohort 1 – single a	scending dose,	3-way crossover): Vital Signs	•	
32.	Safety (Part A)	VS5	Listing of All Vital Signs Values for Subjects with Any Value of Potential Clinical Importance (Part A)	IDSL Footnote: Note: For absolute results: H=High, L=Low. For change from baseline: H1=Lower Increase, H2=Upper Increase, L1=Lower Decrease, L2=Upper Decrease.	SAC
33.	Safety (Part A)	VS5	Listing of Vital Signs Values of Potential Clinical Importance (Part A)	IDSL Footnote: Note: For absolute results: H=High, L=Low. For change from baseline: H1=Lower Increase, H2=Upper Increase, L1=Lower Decrease, L2=Upper Decrease.	SAC

ICH: Lis	tings				
No.	Population	IDSL / Example Shell	Title	Programming Notes	Deliverable [Priority]
Part B (Cohorts 2, 3, 4 and	5 – repeat dose	, sequential-group): Disposition	·	
40	All Subjects (Part B)	ES7	Listing of Reasons for Screen Failure (Part B)	Journal Guidelines	SAC
41	Safety (Part B)	ES2	Listing of Reasons for Study Withdrawal (Part B)	ICH E3	SAC
42	Safety (Part B)	SD2	Listing of Reasons for Study Treatment Discontinuation (Part B)	ICH E3	SAC
43	Safety (Part B)	BL1	Listing of Subjects for Whom the Treatment Blind was Broken (Part B)	ICH E3	SAC
44	Safety (Part B)	TA1	Listing of Planned and Actual Treatments (Part B)	IDSL	SAC
Part B (Cohorts 2, 3, 4 and	5 – repeat dose	, sequential-group): Protocol Deviations	·	
45	Safety (Part B)	DV2	Listing of Important Protocol Deviations (Part B)	ICH E3	SAC
46	Safety (Part B)	IE3	Listing of Subjects with Inclusion/Exclusion Criteria Deviations (Part B)	ICH E3	SAC
Part B (Cohorts 2, 3, 4 and	5 – repeat dose	, sequential-group): Populations Analysed		

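### SAP section 4 classifies the Safety population by randomised treatment, protocol 10.3 by treatment received, and SAP Table 1 does not declare the change

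*SAP*

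**What the plan says.** Protocol 10.3 defines the Safety population as everyone randomised who took at least one dose, and adds: "Participants will be analyzed according to the treatment they actually received".

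SAP section 4 keeps the same membership but changes the classification: "This population will be based on the treatment the subject was randomised to".

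SAP 2.1, Table 1, has two entries. One drops the formal interim analysis. The other replaces the Enrolled population of protocol 10.3 by a Randomised population, with the rationale "The population was renamed to match the current IDSL guidance". Neither concerns the Safety population.

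SAP 10.5.2, under Formats, sets a general default: "All data will be reported according to the actual treatment the participant received, unless otherwise stated".

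A footnote to Table 1.6 in SAP Appendix 10 reads "Subjects are included in the Safety population if they have been randomized and received at least one dose of study treatment". It says who belongs to the population, not which treatment they are counted under.

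**The concern.** Safety is the primary objective, and SAP section 6 runs all safety analyses on the Safety population unless otherwise specified. If a participant received something other than the assigned treatment, following section 4 would count that participant's events under a treatment not taken. The error can go either way: an event on active drug shown under placebo, or the reverse.

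As the SAP stands, a programmer following section 4 and one following 10.5.2 would build different tables, and the document does not say which rule governs. The PK population is a subset of Safety and states no treatment basis of its own, so the ambiguity may carry over to it.

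The SAP contains a note in section 5.1 written after Cohort 4 ended, and the sponsor was unblinded throughout. Nothing suggests intent, but a classification rule that departs from the protocol at that stage should be visible and justified.

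**Working it through.** **Text.** The comparison, place by place:

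| Place | Membership of Safety | Treatment basis |
|---|---|---|
| Protocol 10.3 | randomised, at least one dose | received |
| SAP section 4 | same | randomised |
| SAP 2.1 Table 1 | not mentioned | not mentioned |
| SAP 10.5.2 | none stated | received, unless the SAP says otherwise |
| SAP Table 1.6 footnote | randomised, at least one dose | none stated |

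The first two rows cannot both be followed for a mis-dosed participant. Section 4 is a specific contrary statement, so the default in 10.5.2 most naturally yields to it. Table 1 does address protocol 10.3, but only for the Enrolled population.

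**The plan's own figures.** Protocol 10.1 gives exact 95% upper limits of 33.6% for 0/9 and 48.2% for 1/9. The two-sided Clopper-Pearson limit gives 33.63% and 48.25%, so both reproduce. The concern does not dispute them.

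**Column sizes.**

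- Part A: sequences ABC, ABP, APC and PBC, assuming 3 of the 12 participants in each and no replacements. Each of A, B, C and P appears in three sequences, so each column has 3 × 3 = 9.
- Part B 240 mg TID: 9, from the 9:5 allocation in Cohort 4.
- Part B 120 mg TID: SAP 5.1 gives the code for "GSK2982772 Cohort 3 Repeat Dose" the same display label as the Cohort 2 dose, so the two are pooled. Cohort 3 gives 9. Cohort 2 is assumed to give 1 (the active sentinel) to 9 (full 3:1 allocation of 12). Total 10 to 18.
- Part B placebo: 5 + 5 from Cohorts 3 and 4, plus an assumed 1 to 3 from Cohort 2. Total 11 to 13. SAP 5.1 records that Cohort 5 was not required.

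The Cohort 2 counts are assumptions because the Amendment 02 rationale says only its two sentinels completed dosing, not how many started.

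**One participant's share of a column, 100/n, and the shift when a participant with an event joins a column with no other events, 100/(n+1).**

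| Column | n | 100/n | 100/(n+1) |
|---|---|---|---|
| Part A, any regimen or placebo; Part B 240 mg TID | 9 | 11.1 | 10.0 |
| Part B 120 mg TID, pooled | 10 to 18 | 10.0 to 5.6 | 9.1 to 5.3 |
| Part B placebo, pooled | 11 to 13 | 9.1 to 7.7 | 8.3 to 7.1 |

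**Illustration (assumed error).** In a 9:5 cohort, one participant randomised to placebo takes active drug and has the only event. Exact 95% upper limits:

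- As randomised (SAP section 4): active 0/9, 33.6%; placebo 1/5, 71.6%.
- As received (protocol 10.3): active 1/10, 44.5%; placebo 0/4, 60.2%.

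The as-randomised table would show no event on active drug.

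**The case against.** The best defence is that 10.5.2 governs the displays. On that reading section 4 describes only what the population is based on, the tables would be built by actual treatment, and the SAP already agrees with the protocol. The Safety sentence nearly repeats the one in the Randomised row above it, so it may be a carry-over with no intended change to declare.

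That reading is available, and the carry-over is plausible, though it is an inference. Neither removes the problem: 10.5.2 gives way to contrary statements, section 4 is one, and a drafting slip in the definition behind the primary tables still needs correcting.

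Several limits do stand:

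- The share 100/n is not the shift when someone joins a column; that is 100/(n+1).
- Those sizes need a whole Part A period, or a Part B course, to be attributed to another treatment.
- The documents report no mis-dosing, but a protocol and SAP would not normally do so, which is weak reassurance. Better reassurance comes from central randomisation and supplies labelled by randomisation number (protocol 7.2), and from second-person checks of preparation, dose and identity (protocol 7.5).
- No hypotheses are tested. A mis-dosing would still show in Listings 5 and 44, which set planned against actual treatment, and in the adverse event listings.

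**Conclusion.** The concern holds. SAP section 4 contradicts protocol 10.3 on how the Safety population is classified, conflicts with the SAP's own default in 10.5.2, and is not declared in Table 1. It is wrong as written.

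The severity is minor. There is no numerical effect if everyone received the assigned treatment. Otherwise one misclassified participant is 11.1 points of a column of 9 and 5.6 to 10.0 points of the larger pooled columns. Those sizes rest on equal allocation to the Part A sequences, no replacements, and the assumed Cohort 2 counts. The textual conflict rests on none of these.

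**What to change.** In SAP section 4, state that the Safety population is analysed by the treatment actually received, and in Part A by the treatment actually received in that period. This agrees with protocol 10.3 and SAP 10.5.2. The per-period clause is an addition to both, in line with the period-based study phases in SAP 10.4.1. Keep the as-randomised rule for the Randomised population, which serves only the age-range tables.

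If as-randomised is really intended for safety, declare it with a rationale in SAP Table 1 and name it as the exception to 10.5.2.

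The cost is one sentence, and actual treatment is already planned in the data for Listings 5 and 44. The change does not settle how to classify a Part B participant given a few wrong doses among the 14 × 3 = 42 planned TID doses. Protocol 10.3 leaves that open too.
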